7 PROTOCOL SYNOPSIS

Protocol title	A double-blind, multi-center, two-part, randomized, placebo-controlled study of the safety, tolerability, and efficacy of 4 weeks of treatment with AP1189 in early rheumatoid arthritis (RA) patients with active joint disease
Protocol no	SynAct-CS002
Clinical phase	Ila
Estimated study duration	Study duration: 18 months Study participation for each subject is estimated to 10 weeks
Study design	A multicenter, two-part, randomized, double-blind, placebo-controlled, 4-week study with repeated doses of AP1189. The study population will consist of newly diagnosed subjects with severe active RA (CDAI (Clinical disease activity score) > 22) who are to start up-titration with methotrexate (MTX).
	Part 1: The subjects will be randomized into:
	 Group A: AP1189 dose 50 mg (min. 8 subjects) or Group B: placebo (min. 4 subjects)
	Steering Committee (SC) meeting
	 Group C: AP1189 dose 100 mg (min. 8 subjects) or Group D: placebo (min. 4 subjects)
	INTERIM ANALYSIS
	Part 2: All subjects will be randomized into either design 1, 2 or 3 based on data from the interim analysis.
	 Design 1: AP1189 dose 50 mg (44 subjects) or placebo (22subjects) plus MTX (10-25 mg) weekly Design 2: AP1189 dose 100 mg (44 subjects) or placebo (22 subjects) plus MTX (10-25 mg) weekly Design 3: Continue with the same doses as in Part 1, in a 1:1:1 ratio (AP1189 50 mg (22 subjects), AP1189 100 mg (22 subjects) or

Protocol Code Number: SynAct-CS002

	placebo (22 subjects)) plus MTX (10-25 mg) weekly
Study sites	The study is to be conducted at sites in Europe and Moldova
Treatment duration	Multiple dose administration consisting of once- daily dosing from Day 1 to Day 28, preceded by a screening period of up to 2 weeks before the first dosing. A 4 weeks safety follow-up period will follow the last dose administration
Study population	Subjects with severe active RA, defined as CDAI > 22, who are about to begin up-titration with MTX
Study objectives	Primary safety objective: • To compare the safety of AP1189 against placebo by evaluating adverse events (AEs), serious adverse events (SAEs), and laboratory abnormalities
	 Primary efficacy objective: Effect of AP1189 vs. placebo in subjects with severe active RA (CDAI > 22), undergoing up-titration with MTX, by showing a change in CDAI from severe (CDAI > 22) to moderate (CDAI ≤ 22) after 4 weeks treatment compared to baseline

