22 SAFETY

Adverse events will be monitored from the time that the subject gives informed consent and throughout the study, and will be elicited by direct, non-leading questioning or by spontaneous reports. Further details for AE reporting can be found in section 18.4.

Conditions that started before signing the informed consent and for which no symptoms or treatment are present until the first administration of study drug (e.g., seasonal allergy without acute complaints), are recorded as medical/surgical history.

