22.4 Reporting Procedures of Adverse Events

The responsible for ensuring that all AEs (as defined in Section 18.1) observed by the staff at the clinic or reported by subjects are collected and recorded in the subject's medical notes and the eCRF. The condition of each subject will be monitored throughout the study.

All AEs will be reported starting from the time informed consent for study participation is provided and until the final visit (End of Study/Early Termination visit) has occurred. All AEs that are ongoing at the subject's last visit must be followed until resolution or for 4 weeks after the study drug administration, whichever comes first.

A cluster of signs and symptoms that results from a single cause should be reported as a single AE (e.g., fever, elevated WBC, cough, abnormal check x-ray, etc. can all be reported as Pneumonia). The investigator must assign the following adverse event attributes: adverse event diagnosis or syndrome(s) (if known, signs or symptoms if not known); dates of onset and resolution; severity; assessment of relatedness to investigational product and action taken.

Protocol Code Number: SynAct-CS002

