### **3.2** Analysis Data Sets

The sets of subjects to be analyzed are defined as follows:

- The safety analysis set consists of all subjects who received the study medication at least once, analyzed by received treatment.
- The **pharmacokinetic (PK) analysis set** consists of all subjects who completed the study and did not have any protocol deviation or events implying a bias for the PK evaluation.
- The efficacy analysis set consists of all randomized subjects who received the study medication at least once, analyzed by randomized treatment (intention to treat). A second analysis of the primary efficacy endpoint, for robustness, will be performed for all randomized subjects who complete the study without any major protocol violations (per protocol).

All safety and tolerability analyses will be conducted on the safety data set, all PK analyses will be conducted on the pharmacokinetic data set, and all efficacy analyses will be conducted on the efficacy data set.

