## 7 SAFETY AND TOLERABILITY ANALYSES

All safety parameters (vital signs, ECG, AEs/SAEs, laboratory abnormalities, etc.) will be summarized by treatment as well as for all subjects in total, by time point. Individual subject listings will also be prepared for all safety variables. Listings will include flagging of clinically notable vital sign abnormalities, as defined in protocol Table 5.

Patients with no post randomization data who cannot be contacted will not be counted in frequency tables. If included, such patients would reduce the frequency of Adverse Events.

Patients will be tabulated according to treatment received. Patients who have not received any trial medication (neither active treatment nor placebo) will not be included in frequency tables.

Variables are listed below (CRF annotation presented in parenthesis), along with a short description of how they will be presented.

For a list of proposed tables, see Appendix 4.

Study SynAct-CS002 – Statistical Analysis Plan

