| Phase of study at time of event (SAESP)                                       | # patients and % /category (4 categories:
Screening/Treatment/Wash-out/Follow-up),
included in SAE table   |
| Study Drug Information (SAESD, SAEFREQ, SAEFADT, SAELADT)                     | Listing only   |
| SAE abate after stopping study medication (SAEDECH)                           | Listing only   |
| SAE reappear after reintroduction of study medication (SAERECH)               | Listing only   |
| Blinding code broken (SAEBBROK, SAEBBDT)                                      | Listing only   |
| Concomitant medication (SAECM)  | Listing only   |
| Relevant medical history (SAEMH)  | Listing only   |
| Hospitalisation Details (SAEHOSP, SAEADT, SAEDDT)                             | Listing only   |
| Death Details (SAEDEDT, SAEPCAUS, SAEAUTO, SAEINF)                            | Listing only   |

The incidence of AEs will be summarized by the reported AE term. A subject will be counted only once in the incidence count for a specific AE term, although an AE term might be reported more than once for a particular subject.

Separate summaries will be provided for relationship (yes, no) to study drug. An AE will be considered related to study drug if the investigator reported the event to be "definitely, probably, possibly, or unlikely" related to treatment on the CRF.

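### The AE incidence and severity counts by treatment have no onset-after-first-dose rule, so non-serious events from screening can enter both the AP1189 and the placebo columns

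*SAP*

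**What the plan says.** **Collection.** Protocol 22.4 states: "All AEs will be reported starting from the time informed consent for study participation is provided". The opening of Protocol 22 agrees: "Adverse events will be monitored from the time that the subject gives informed consent and throughout the study". Events between consent and first dose are therefore recorded as AEs. The synopsis describes treatment as "preceded by a screening period of up to 2 weeks before the first dosing" and adds: "A 4 weeks safety follow-up period will follow the last dose administration".

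**Analysis.** The safety set in SAP 3.2 is "all subjects who received the study medication at least once, analyzed by received treatment". That selects subjects, not events. SAP 7 says: "All safety parameters (vital signs, ECG, AEs/SAEs, laboratory abnormalities, etc.) will be summarized by treatment", and by time point. SAP 7.10 summarises incidence by reported term, and "A subject will be counted only once in the incidence count for a specific AE term". Neither section refers to onset relative to first dose. The AE start date (AESTDAT) is collected but goes only to a listing.

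**Treatment-emergent.** The SAP body does not define the term. The protocol expands TEAE in its glossary and uses it for Phase 1 results. The spelled-out term appears otherwise only in the definition of prolonged hospitalisation in Protocol 22.1.

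**Text that points the other way.** The flow chart (Protocol section 20, Table 3) first marks AE recording at Baseline. Protocol 22.5 starts SAE reporting at first dose, yet the SAE table in SAP 7.10 has a study-phase variable with a screening category.

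**The concern.** The primary safety objective compares AP1189 with placebo on AEs, SAEs and laboratory abnormalities. An event that began before first dose cannot have been caused by the study drug, so in a by-treatment table it tells the reader nothing about the drug.

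Two things can go wrong under the counting rule as written. First, such an event is counted under the arm the subject later joined, which raises incidence in both arms. Second, if the count runs over the study, a subject with headache in screening is already counted for headache, and a new headache on treatment adds nothing. Both effects make the arms look more alike in relative terms, which is the less cautious direction for a safety comparison.

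**Working it through.** The documents give no figure to reproduce for this point, so the check covers the observation window and then the size of the effect.

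**Window.** Screening up to 14 days + treatment 28 days + follow-up 28 days = 70 days = 10 weeks, which matches the participation time in the synopsis. For a screening period of s days, the pre-dose share is s/(s + 56): 1/57 = 2%, 7/63 = 11%, 14/70 = 20%.

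**Rate ratio.** Assume a constant background rate, and a true rate ratio of 1.50 over the 56 days after first dose. Pre-dose days carry the background rate in both arms, so

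observed ratio = (s + 56 × 1.5)/(s + 56) = (s + 84)/(s + 56).

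| Screening days | Observed ratio |
|---|---|
| 1 | 85/57 = 1.49 |
| 7 | 91/63 = 1.44 |
| 14 | 98/70 = 1.40 |

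If the excess is confined to the 28 treatment days, the ratio after first dose is (42 + 28)/56 = 1.25, and 14 days of screening bring it to (14 + 42 + 28)/70 = 1.20.

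**Subjects counted once.** The SAP reports numbers and percentages of patients, so the second calculation uses incidence. Let p0 be the placebo incidence of one term over 56 days and assume a true risk ratio of 2.0, so p1 = 2 × p0. With a constant hazard, the chance of a pre-dose event is pre = 1 − (1 − p0)^(s/56). Assuming pre-dose and post-dose events are independent, the counted incidence is q = 1 − (1 − p)(1 − pre) in each arm. For s = 14:

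| p0 | pre | Placebo counted | AP1189 counted | Ratio | Difference: true → counted, points |
|---|---|---|---|---|---|
| 5% | 1.27% | 6.21% | 11.15% | 1.79 | 5.0 → 4.9 |
| 10% | 2.60% | 12.34% | 22.08% | 1.79 | 10.0 → 9.7 |
| 20% | 5.43% | 24.34% | 43.26% | 1.78 | 20.0 → 18.9 |

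With 7 days of screening the ratio is 1.88 to 1.89, and with 1 day 1.98. The difference shrinks only by the factor (1 − pre), for example 10.0 × (1 − 0.026) = 9.7. That shrinkage is the masking effect: subjects already counted before first dose.

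**Subjects affected.** Over these values of p0 and s = 1 to 14 days, the expected number with a pre-dose event of one given type is 30 × pre = 0.03 to 1.6 per 30-subject arm (the minimum in Protocol 23.2.1). One such subject more in one arm than in the other shifts the comparison by 1/30 = 3.3 points. In a 15-subject sub-study arm (Protocol 23.2.2) the shift is 1/15 = 6.7 points.

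**The case against.** Much of the opposing case stands, and it sets the limits of the point.

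- **Metric.** The SAP plans counts and percentages, not AE ratios. Equal background in both arms barely moves a difference in percentages, as the last column of the second table shows. A reader might infer that any true difference is pulled substantially towards zero. That holds for ratios, not for the planned percentages.
- **Direction.** Randomization follows screening, so pre-dose events are balanced in expectation. Nothing in the documents supports a systematic bias for or against AP1189.
- **SAEs.** Reporting starts at first dose (Protocol 22.5) and the SAE table shows study phase, so a pre-dose SAE would be rare and visible.
- **Relationship and action.** Under Protocol 22.3 an event with no plausible timing belongs in the lowest relationship category, which falls outside the related-AE summary. The action table has a not-applicable category. A reader might extend the concern to the SAE and drug-related summaries, but these passages largely protect them.
- **Timing of recording.** If sites follow the flow chart and start at Baseline, fewer pre-dose events are captured. This does not remove them: Baseline is Day 0 with dosing from Day 1, and AE recording shares that visit with randomization and first dispensing.
- **By-visit tables.** Events recorded at Baseline can be read separately there, though still in a treatment column. SAP 7.10 states no period for the once-per-subject count, so it cannot be taken as fact that it runs over the whole study. The masking effect depends on that reading.
- **Table shells.** SAP Appendix 4 is a separate document and was not available. A restriction there cannot be excluded, but the SAP body states the counting rule without one.

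**Conclusion.** The point holds for non-serious AE term incidence and severity by treatment. As written, the SAP lets events with onset before first dose into those counts and may let them mask the same term on treatment. The consequence is modest: inflated incidence in both arms, chance imbalance in small arms, diluted ratios and a slightly smaller absolute difference. The figures rest on assumed inputs (constant background rate, independence, chosen incidences and risk ratio). Fourteen days is the longest screening allowed, so 1.40 is the far end of a range that starts at 1.49, not a typical value. A change is still worth making, because it bears on the primary safety objective and the data needed are already collected.

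**What to change.** In SAP 7.10, base the by-treatment AE term incidence and severity tables on treatment-emergent AEs:

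- AESTDAT on or after the date of first IMP intake, taken from the diary. The comparison is by date because no AE onset time is listed, so a same-day event counts as treatment-emergent.
- Or a pre-dose AE re-reported as worsened after that date. No separate worsening date is listed, so the new report has to supply it.
- Events that cannot be dated count as treatment-emergent.
- AEs with onset before first dose go in a separate listing.

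Separately, reconcile the start of AE and SAE recording across the flow chart, Protocol 22, 22.4 and 22.5, and the screening category of the SAE table in SAP 7.10.

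The cost is one derived flag and one extra listing. Stated AE percentages become slightly lower, and no recorded event is lost from the report.

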22.3 Relationship to Study Drug

A determination will be made of the relationship (if any) between an adverse event and the study drug. A causal relationship is present if a determination is made that there is a reasonable possibility that the adverse event may have been caused by the study drug.

The investigator should determine the relationship of an AE to the study drug after thorough consideration of all facts that are available and will be assessed using the following definitions:

- **Definitely not related**: Temporal relationship to study drug administration is missing or implausible, or there is an evident other cause
- **Probably not related**: Temporal relationship to study drug administration makes a causal relationship improbable; and other drugs, chemicals, or underlying disease provide plausible explanations
- **Possibly related**: The AE occurred in a reasonable time after study drug administration but could be related to an underlying disease, environmental or toxic factors, or other drug or therapy
- **Probably related**: Reasonable time sequence to the administration of study drug and unlikely to be attributed to concurrent disease or the drugs or chemicals, and which follows a clinically reasonable response on withdrawal (dechallenge). Rechallenge information is not required
- **Definitely related**: Plausible time relationship to study drug administration and event cannot be explained by concurrent disease or other drugs or chemicals. The response to withdrawal of the drug (dechallenge) should be clinically plausible. The event must be definitive pharmacologically or phenomenologically, using a satisfactory rechallenge procedure if necessary

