### 3.12 Documentation and Other Considerations

Protocol Section 12.2 Primary efficacy Objective states "Effect of AP1189 vs. placebo in subjects with severe active RA (CDAI > 22), undergoing up-titration with MTX, by showing a change in CDAI from severe (CDAI > 22) to moderate (CDAI  $\leq$  22) after 4 weeks treatment compared to baseline." The cut-off values for the CDAI score correspond to severe (CDAI>22) or moderate **or lower** (CDAI  $\leq$  22), which is the wording used in this analysis plan.

Protocol Section *12.3 Secondary efficacy Objectives* states that the "Proportion of subjects achieving American College of Rheumatology (ACR) response assessed by ACR20, ACR50, and ACR70" will be assessed. These responses will be assessed at week 4 compared with baseline (no time point was specified in the protocol).

Protocol Section 12.4 Tertiary Efficacy Objectives states that the "Effect of AP1189 compared to placebo at week 4 compared to baseline on inflammatory and collagen destructive biomarkers" will be assessed. The comparison to baseline will be made by calculating the change for these biomarkers (CXCL13, IL-1 $\beta$ , IL-6, IL-10, and TNF- $\alpha$ ) at week 4 compared with baseline (the calculation of a change from baseline was not specified in the protocol). In addition, the ratio IL-6/IL-10 will be evaluated in the same way.

Protocol Section 23.6 Pharmacokinetic Analyses states that "Descriptive statistics will be used for an exploratory description of exposure in relation to effect." However, only one sample is taken at each visit (for some visits), with variability in the time from last dosing to sampling. Thus, the relationship between exposure and effect is not possible to evaluate, and exposure will therefore be described without relation to effect..

No other changes to analyses specified in the protocol have been identified at the time of writing this SAP.

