## 7.10 Adverse Events

| Variable (CRF annotation)               | How to be presented  |
|---|--|
| Any new (or changes to) AE (AEYN)       | # patients and % /category
(2 categories: Yes/No), by visit   |
| AE description/Term (AETERM)            | Listing only (used for MedDRA coding)  |
| AE MedDRA term (coding performed by DM) | # patients and % /MedDRA term
(x categories), by visit  |
| AE start date (AESTDAT)                 | Listing only   |
| AE end date (AEENDAT)                   | Listing only   |
| AE ongoing (AEONG)                      | Listing only   |
| Date site aware of AE (AEAWDT)          | Listing only   |
| AE severity (AESEV)                     | <pre># patients and % /category (5 categories: Mild/Moderate/Severe/Life- threatening/Death), by visit</pre>   |
| Relationship to study treatment (AEREL) | # patients and % /category
(5 categories: Definitely not related/Probably
not related/Possibly related/Probably
related/Definitely related), by visit   |
| Action taken with study drug (AEACT)    | # patients and % /category
(5 categories: Dose not changed/Dose
interrupted/Drug withdrawn/Not applicable/
Unknown), by visit   |
| AE outcome (AEOUT)                      | 
 
# patients and % /category
 
(6 categories: Fatal, Not recovered/Not
Resolved, Recovered/Resolved,
 
Recovered/Resolved with sequelae,
 
Recovering/Resolving
 
Unknown), by visit
 
 |
| Medication given to treat AE (AETREAT)  | # patients and % /category
(2 categories: Yes/No), by visit   |

| Serious Adverse Event (AESER, AESER1, AESER2, AESER3, AESER4, AESER5, AESER6) | 
 
# patients and % /category
 
(2 categories for AESER: Yes/No, plus number of
each kind of SAE: Death, Life-threatening,
Inpatient hospitalisation or prolongation of
existing hospitalisation, Persistent or significant
disability/incapacity, Congenital anomaly or
birth defect, and/or Important medical event),
by visit
 
 |
|---|--|
| SAE report Date (SAEREPDT)  | Listing only   |
| Date of birth (BRTHDT)  | Listing only   |
| Sex (GENDER)  | Listing only   |
| Height, cm (HEIGHT, AE dataset)   | Listing only   |
| Weight, kg (SAEWGHT)  | Listing only   |
| SAE description (SAEDESC)   | Included in SAE table  |

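### The SAP's yes/no rule for drug-related AEs includes 'unlikely', a category the trial does not collect, so it does not fix a single related-AE table

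*SAP*

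**What the plan says.** SAP 7.10 gives two specifications for causality.

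- The variable table lists AEREL, the relationship to study treatment, as patient counts and percentages by visit over "5 categories: Definitely not related/Probably not related/Possibly related/Probably related/Definitely related".
- The text after the table adds a dichotomy: "Separate summaries will be provided for relationship (yes, no) to study drug". It counts an AE as related if the CRF rating is "definitely, probably, possibly, or unlikely" related to treatment. A subject is counted once per AE term.

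Protocol 22.3 defines the same five categories. It treats a causal relationship as present when "there is a reasonable possibility that the adverse event may have been caused by the study drug". Two adjacent definitions matter here:

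- 'Probably not related': "Temporal relationship to study drug administration makes a causal relationship improbable", with other drugs, chemicals or underlying disease as plausible explanations.
- 'Possibly related': "The AE occurred in a reasonable time after study drug administration but could be related to an underlying disease", or to other causes, including another drug or therapy.

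SAP 3.12 lists departures from the protocol. None concerns AE relatedness, and the section closes with "No other changes to analyses specified in the protocol have been identified at the time of writing this SAP".

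**The concern.** The dichotomy is written for a scale that differs from the one the SAP itself says is collected. 'Unlikely' appears neither in the AEREL list nor in Protocol 22.3, so a programmer must decide what to do with it. One natural choice is to take the word as the step just below 'possibly', which on this scale is 'Probably not related'. That choice puts a category carrying the label 'not related' into the related count.

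Comparing the safety of AP1189 with placebo is the primary safety objective, and related AEs are a summary readers will look at. An undeclared rule that may include events the investigator judged improbable as drug effects can raise the related count in all arms, placebo included. The table would then disagree with the causality ratings behind it. The SAP's introduction says the plan exists to avoid post hoc decisions that could affect interpretation, yet this sentence leaves one open.

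**Working it through.** The plan gives no figure to reproduce. The check is a term-by-term comparison of the SAP 7.10 rule with the AEREL categories listed in the same section and defined in Protocol 22.3.

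| Term in the SAP rule | AEREL category | Match |
|---|---|---|
| definitely (related) | Definitely related | yes |
| probably (related) | Probably related | yes |
| possibly (related) | Possibly related | yes |
| unlikely (related) | none; nearest is Probably not related | no |

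**Reading A: 'unlikely' is mapped to 'Probably not related'.** Related = Definitely, Probably, Possibly and Probably not related: 4 of 5 categories. Only 'Definitely not related' counts as no. The added category is the one the protocol defines by an improbable causal relationship, which falls short of its reasonable-possibility threshold.

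**Reading B: 'unlikely' is matched literally.** No record carries that value, so related = Definitely, Probably and Possibly related: 3 of 5 categories. This is consistent with Protocol 22.3.

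**Difference between the readings.** For one arm with n subjects, let k be the number whose highest AEREL rating is exactly 'Probably not related' (overall, or within one AE term for a term-level table). Then:

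- related subjects under A − related subjects under B = k, which is zero or more in every arm;
- change in the AP1189-minus-placebo difference in related proportions = k(AP1189)/n(AP1189) − k(placebo)/n(placebo), which can take either sign.

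The documents give no k for any arm. The size of the inflation and its effect on the between-arm comparison therefore cannot be computed from them.

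**Is it a declared choice?** SAP 3.12 records no departure on this point. The SAP revision history shows no change to the sentence, so it appears to date from version 1.0, the version SAP 3.7 says was used for the interim analysis. SAP 3.7 also names related adverse events among the safety profiles listed for that analysis. It does not say whether the yes/no rule was applied there.

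**The case against.** The strongest reply is that the rule does no harm if followed to the letter: 'unlikely' matches nothing and the three genuinely related categories remain. That is correct. A reader might infer that the related-AE table is wrong as written, but the documents do not support this. The specification is faulty, while the numbers are wrong only under Reading A. The documents also do not state which reading the author intended.

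Other parts of the reply also stand:

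- Protocol 22.3 sets a causality threshold and five labels but no analysis dichotomy, and Protocol 23.4 plans no yes/no related summary. The three-against-two split is a strong inference from the labels and definitions; it is not protocol text.
- The damage is contained. The five-category AEREL table and the individual listings would expose a misclassification. SARs and SUSARs are classified from the investigator's judgement, and the Part 2 design criteria in Protocol 15.10 do not use relatedness. The analysis is descriptive, so no test depends on this table.
- SAP Appendix 4, with the table specifications, is a separate document not available here and may settle the mapping. The CRF was not seen either; its categories are taken from the SAP's annotation.

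Three further inferences are tempting and should not be drawn:

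- *Many events will be rated 'Probably not related' because all subjects start methotrexate.* No passage gives such a frequency, and the definition of 'Possibly related' also covers events that may be due to another drug.
- *The effect can be sized from Phase 1 Part IV, where 4 of 35 TEAEs were considered possibly related.* The documents do not split the other 31 or say that this scale was used. Those subjects were healthy volunteers, and the figure counts events where the SAP counts subjects.
- *'Definitely' and 'probably' could pick up the two 'not related' labels.* The SAP sentence says related to treatment, so that reading is not reasonable.

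What the reply does not remove is that the sentence names an uncollected value and two programmers could follow it to different tables.

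**Conclusion.** The concern holds as an internal inconsistency in a derived-variable definition. The SAP 7.10 rule does not determine one yes/no related-AE table: it yields three of five categories read literally, or four of five if 'unlikely' is mapped to its nearest counterpart. The four-category version is inconsistent with the Protocol 22.3 threshold and can inflate related counts in every arm. By how much is unknown.

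The conclusion rests on the SAP's own CRF annotation being accurate and on Appendix 4 not already defining the mapping. The matter should be fixed because the remedy costs almost nothing. It is not critical, since the full five-category distribution is reported and no decision rule uses the dichotomy.

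**What to change.** Replace the definition in SAP 7.10 with: 'An AE is considered related if AEREL is Possibly related, Probably related or Definitely related; Probably not related and Definitely not related are not related.' This is consistent with Protocol 22.3. Make the change before unblinding, or record it as a correction if unblinding has already taken place. Align the Appendix 4 table specifications if they repeat the old wording.

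Then check whether any related-AE output already produced, including for the interim analysis, used a four-category rule, and regenerate it only if it did. If a four-category rule was intended as a conservative choice, it should be stated in the collected category names and declared in SAP 3.12.

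The cost is one sentence in the SAP, one line of code and a short check of existing outputs.
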